# PPD

Parameter	Calculation
reduction in HbA1c > 0.5% from baseline and daily insulin requirement <0.50 IU/Kg/day at Time point Tx	at Time point T x : 

if HbA1c reduction <math>\leq 0.5\%</math> OR daily insulin requirement <math>\geq 0.50</math> IU/Kg/day, then endpoint = 'No' (even in case of one missing component)

if HbA1c reduction <math>> 0.5\%</math> AND daily insulin requirement <math><0.50</math> IU/Kg/day, then endpoint = 'Yes' (both component should be non-missing)

Conversion of Time Intervals	If a time interval was calculated in minutes, hours or days and needs to be converted into months or years the following conversion factors will be used: 

1 week = 7 days

1 month = 30.4375 days

1 year = 365.25 days

## 9.2 CGM value derivation

The Dexcom G6 Continuous Glucose Monitoring System (Dexcom G6 System) will be used to perform CGM during the study. Dexcom G6 System uses proprietary algorithms to create fully customizable reports and summary measures for patients and clinicians. These reports will not be used during the trial given the fully customizable features. Instead, in order to standardize the summary statistics from each patient, the *cgmanalysis* package written entirely in the statistical programming language R (R Foundation for Statistical Computing, Vienna, Austria) will be used given its compatibility with raw data structure coming from Dexcom G6 System.

Gaps in glucose data shorter or equal than 30 minutes will be imputed using linear interpolation. The *cgmanalysis* package cleandata function will be used.

After filling eventual gaps in the glucose data, the following requirements should be met for a visit in order to be considered eligible for analysis:

- a total of at least 7 days of valid CGM recordings will be required for a visit to be used for analysis (by study protocol, at least 10 days before each scheduled visit the CGM sensor should be positioned):
  - *cgmanalysis*: num\_days\_good\_data  $\geq 7$ ;
- the number of sensor readings as a percentage of the number of potential readings (given time worn) has to be greater than 80%:
  - *cgmanalysis*: percent\_cgm\_wear  $> 80\%$ .

The *cgmanalysis* package *cgmvariables* function will be used for the CGM parameters (sections 7.2.1.4 and 7.2.1.7). The package has been modified in order to perform additional simultaneous analyses (see Appendix 12.1 for the entire R code). Table 5 reports the correspondence between required endpoint and *cgmvariables* outcomes.

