# PPD

R code	Notes
<pre> if(printname == T) {   print(basename(files[f])) }  # Column names to lower case colnames(table) = tolower(colnames(table)) cgmupload["subject_id",f] <- table\$subjectid[1] # Format columns. table\$timestamp <-   base::as.POSIXct(lubridate::parse_date_time(table\$timestamp,   dateparseorder,tz = "UTC")) table\$sensorglucose <- suppressWarnings(base::as.numeric(table\$sensorglucose)) interval <- pracma::Mode(base::diff(base::as.numeric(table\$timestamp))) interval <- base::abs(interval) cgmupload["date_cgm_placement", f] <-   base::as.character(min(table\$timestamp,na.rm = T))  totaltime <-   base::as.numeric(base::difftime(base::max(table\$timestamp, na.rm = T),                                    base::min(table\$timestamp,na.rm = T),                                    units = "secs")) cgmupload["percent_cgm_wear",f] <-  base::floor(((base::length(which(!is.na(table\$sensorglucose)))/(totaltime/interval))*100)) cgmupload["num_days_good_data",f] <-   base::round(base::length(which(!is.na(table\$sensorglucose)))/(86400/interval))  table <- table[!is.na(table\$timestamp) & !is.na(table\$sensorglucose),]  cgmupload["total_sensor_readings",f] <-   base::as.numeric(base::length(base::which(!is.na(table\$sensorglucose)))) cgmupload["average_sensor",f] <-   base::mean(table\$sensorglucose[base::which(!is.na(table\$sensorglucose))],na.rm = T) cgmupload["estimated_a1c",f] <-   base::round((46.7 + (base::mean(table\$sensorglucose[   base::which(!is.na(table\$sensorglucose))])) / 28.7,digits = 1) cgmupload["gmi",f] <- base::round(3.31 + (0.02392 * base::mean(table\$sensorglucose[   base::which(!is.na(table\$sensorglucose))])), digits = 1) cgmupload["q1_sensor",f] <-   base::as.numeric(base::summary(table\$sensorglucose[   base::which(!is.na(table\$sensorglucose))])[2]) cgmupload["median_sensor",f] <-   base::as.numeric(base::summary(table\$sensorglucose[   base::which(!is.na(table\$sensorglucose))])[3]) cgmupload["q3_sensor",f] <-   base::as.numeric(base::summary(table\$sensorglucose[   base::which(!is.na(table\$sensorglucose))])[5]) </pre>	

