# PPD

R code	Notes
<pre> rl <- table\$rBG[base::which(table\$gluctransform < 0)] rh <- table\$rBG[base::which(table\$gluctransform > 0)] cgmupload["lbgi",f] <- base::mean(stats::na.omit(rl)) cgmupload["hbgi",f] <- base::mean(stats::na.omit(rh)) }  # Write file. cgmupload <-   base::cbind("Variable / Field Name" = rownames(cgmupload),cgmupload) if (format == "rows") {   cgmupload <- base::as.data.frame(base::t(cgmupload))   cgmupload <- cgmupload[-1,] } filename <- base::paste(outputdirectory,"/",outputname,".csv",sep = "") utils::write.csv(cgmupload, file = filename, row.names = FALSE,na = "") } </pre>	
<pre> library(cgmanalysis) library(stringi) library(base)  cleandata(   inputdirectory = "path\\to\\data",   outputdirectory = "path\\to\\cleaned_data",   removegaps = FALSE, gapfill = TRUE, maximumgap = 30)  cgmvariables_mod(   inputdirectory = "path\\to\\cleaned_data",   outputdirectory = "path\\to\\output",   outputname = "Dexcom",   customintervals = list(c(250,400)),   aboveexcursionlength = 35,   belowexcursionlength = 10,   magedef = "1sd",   congan = 1,   daystart = 0,   dayend = 24,   id_filename = F,   format = "rows",   printname = F ) </pre>	
Cleandata will fill in gaps shorter than 30 minutes but will not remove the 24-hour chunks containing larger gaps.
 
Parameters customintervals, aboveexcursionlength, belowexcursionlength, congan, daystart, dayend will not be used.

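### The SAP's CGM eligibility cut-offs (at least 7 days, more than 80% wear) are applied by its own code as more than 6.5 days and at least 81%, because the code rounds one quantity and floors the other

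*SAP*

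**What the plan says.** SAP 9.2 (CGM value derivation) sets two conditions for a visit to enter the CGM analyses. The first is duration: "a total of at least 7 days of valid CGM recordings will be required for a visit to be used for analysis". The second is wear: "the number of sensor readings as a percentage of the number of potential readings (given time worn) has to be greater than 80" per cent. Each is tied to a package variable, `num_days_good_data` (at least 7) and `percent_cgm_wear` (above 80%).

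The order of steps is explicit. "Gaps in glucose data shorter or equal than 30 minutes will be imputed using linear interpolation", and the conditions come next: "After filling eventual gaps in the glucose data, the following requirements should be met for a visit". The `cleandata` call in Appendix 12.1 matches this ("removegaps = FALSE, gapfill = TRUE, maximumgap = 30").

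Appendix 12.1 also prints the two derivations. `num_days_good_data` opens with "base::round(base::length(which(!is.na(table" and is the count of non-missing readings divided by readings per day, rounded to a whole number. `percent_cgm_wear` opens with "base::floor(((base::length(which(!is.na(table" and is the same count as a percentage of potential readings over the recorded span, rounded down. The prose of 9.2 mentions neither operation.

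**The concern.** Rounding before comparing with a threshold moves the threshold. A day count rounded to the nearest integer reaches 7 from just above 6.5. A percentage that is floored first exceeds 80 only from 81. So one test is looser than its wording and the other is stricter.

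The two tests decide which patient-visits contribute to time in range and to the other CGM indices (SAP 7.2.1.4 and 7.2.1.7). Under SAP 4.7, missing continuous values are left out of the summaries, and under 4.8 there is no imputation and no sensitivity analysis. A visit that is wrongly dropped or admitted is therefore not examined anywhere else. A study report that repeated the prose thresholds would misdescribe the visits analysed.

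**Working it through.** **Inputs**
- Thresholds: at least 7 days; more than 80% (SAP 9.2).
- Recording interval: about 5 minutes (protocol Appendix 14.3.4), taken here as exact. Readings per day = 86,400 / 300 = 288.
- Sensor placed at least 10 days before the visit (SAP 9.2), or 14 to 10 days before (protocol Appendix 14.3.4).
- n = non-missing values in the gap-filled file; span = days from first to last timestamp.

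**Day test alone**
- As worded: n / 288 ≥ 7, so n ≥ 7 × 288 = 2,016.
- As coded: round(n / 288) ≥ 7. At n = 1,872 the ratio is exactly 6.5, which R rounds to 6, so it fails. At n = 1,873 the ratio is 6.503, which rounds to 7, so it passes.
- Difference: 2,016 − 1,873 = 143 readings, or 143 × 5 / 60 = 11.9 hours.

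**Wear test alone**
- As worded: 100n / (288 × span) > 80.
- As coded: the floor of that quantity must exceed 80, so it must be at least 81.
- On 10 days (2,880 potential readings) the wording needs 2,305 and the code 2,333. Counts of 2,305 to 2,332 meet the wording and fail the code.
- On 14 days (4,032 potential readings) the corresponding band is 3,226 to 3,265.

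**Both tests together: minimum readings needed**

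| Span (days) | As worded | As coded | Code is |
|---|---|---|---|
| 7 | 2,016 | 1,873 | looser |
| 8 | 2,016 | 1,873 | looser |
| 8.5 | 2,016 | 1,983 | looser |
| 10 | 2,305 | 2,333 | stricter |
| 14 | 3,226 | 3,266 | stricter |

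The full 143-reading leniency is available only while 1,873 readings still give 81% wear, that is for spans up to 1,873 / (288 × 0.81) = 8.03 days. It then shrinks. It is gone once 2,015 readings no longer give 81%, beyond 2,015 / (288 × 0.81) = 8.64 days. On longer spans the code is the stricter of the two.

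**Worked cases**
- 1,880 readings over 8 days: 6.53 days, 81.6%. Fails the wording, passes the code.
- 2,320 readings over 10 days: 8.06 days, 80.6%. Passes the wording, fails the code.
- 1,873 readings over 10 days: 1,873 / 2,880 = 65.0%. Fails both.

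**Second use of the rounded count**

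In Appendix 12.1 `num_days_good_data` also divides `average_auc_70`, `average_auc_180` and `average_auc_per_day`. SAP Table 4 uses these for AUC outside range and for 2-hour PPG. At 1,873 readings the per-day AUC is divided by 7 instead of 6.503, and 6.503 / 7 = 0.929, so it is about 7% too low. At 2,448 readings (8.5 days, which R rounds to 8) it is 8.5 / 8 = 1.0625, so about 6% too high.

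**The case against.** **The printed code is the rule.** SAP 9.2 names the package variables and refers to Appendix 12.1 for the whole program, so anyone can reproduce the eligible set. This stands as far as reproducibility goes. It does not remove the conflict: the same bullets give plain thresholds that the named variables do not apply. The function had already been modified for the AUC below 70 and for CONGA, so the package default was not binding.

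**Gap-filling.** A reader might infer that running the checks on gap-filled data also departs from the SAP, since interpolated values are then counted as readings. The documents do not support that. Section 9.2 prescribes exactly this order and the code follows it. Whether interpolated points in gaps of up to 30 minutes should count as coverage is a design choice. Moving the checks before filling would change the pre-specified rule, and it would need a separate pass over unfilled data, because the function reads files already cleaned.

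**Reach of the two tests.** A reader might also infer that any visit with just over 6.5 days of readings is admitted, or that any patient with 80 to 81% raw wear is lost. Neither follows. The first ignores the wear test, which rejects such a visit on a 10-day recording. The second ignores that the floor acts on wear after filling: raw wear of 80.5% with at least 0.5% of the time in filled gaps reaches 81% and passes.

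**Impact.** Only borderline visits can change, in secondary endpoints, under a SAP version that makes all analyses descriptive (4.8 and 7). This stands, and it limits the importance of the point.

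**Conclusion.** The prose and the code conflict on the two numbers that define an eligible CGM visit. The effective cut-offs are more than 6.5 days and at least 81%, both measured after gap-filling. The day cut-off is looser by up to 143 readings (11.9 hours), in full only on spans up to about 8 days and not at all beyond about 8.6 days. The wear cut-off is stricter by up to one percentage point, which on a 10-day recording is a band of 28 reading counts (2.3 hours). With the planned sensor time of 10 days or more, the wear test is the one that matters. The day test matters only for shortened recordings.

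The figures rest on an exact 5-minute interval. The documents do not give the number of visits near the cut-offs, so the number affected cannot be derived; it is probably small. A reader might infer that the CGM results are materially distorted, and nothing in the documents supports that. This is a minor correction.

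**What to change.** Keep the SAP's order, with eligibility judged after gap-filling, and remove `round()` and `floor()` from the tests. Use the observed modal interval that the code already computes, in place of a fixed 288 per day:

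- readings / (86400 / interval) ≥ 7
- 100 × readings / (totaltime / interval) > 80

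Use the same unrounded day count as the divisor of `average_auc_70`, `average_auc_180` and `average_auc_per_day`, and say so in SAP 9.2. If the sponsor prefers to leave the code alone, the minimum is to restate the cut-offs in 9.2 as more than 6.5 days and at least 81%.

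The cost is two expressions in the code and a sentence or two in the SAP. A few borderline visits would change eligibility in either direction. Per-day AUC outside range would move by a few per cent, up to about 7% at the extremes shown above. The 2-hour PPG value could move more if the function is run on the meal-filtered file. Assuming three meals without overlap, that file holds about 3 × 2 = 6 hours a day, or 2.5 days from a 10-day recording. Rounding that to 2 or 3 changes the divisor by a fifth either way.

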# PPD

For the calculation of 2h PPG, the raw data from Dexcom G6 System have to be filtered in order to keep only observations  $\leq$  120 minutes from meals, where the exact time of meals (breakfast, lunch and dinner) are taken from eDiary. If time of meal is missing, the adjacent CGM observations will not be considered.

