### 14.3.4. Handling of CGM device

The Dexcom G6 Continuous Glucose Monitoring System (Dexcom G6 System) will be used to perform a CGM. CGM measures the subject's interstitial glucose level using electrodes that measure an electric signal produced by glucose oxidase reaction. The system records data approximately every 5 minutes. CGM will be used periodically to measure the subject's interstitial glucose level according to the schedule presented in study flow chart/time and event schedule. A CGM sensor will be inserted subcutaneously at the site 14-10 days before the concerned visits (Baseline, Month 6, 12, 18) and removed during the day of the concerned visit, as per Study Flowchart (see Appendix 14.2).

CGM sensor implantation can occur at Screening Visit and Week 23 Visit if the visit is scheduled 14-10 days before Baseline and before Week 26 respectively. In addition, sites should upload the sensor data to check subject's compliance with wearing the device. The sensor requires at least one SMBG value to be entered every 12 hours for calibration during use. At a minimum, a SMBG value obtained in the morning (e.g. fasting or pre-breakfast measurement) should be entered, as well as a value in the evening (e.g. pre- or post-dinner measurement). Subjects may be instructed to use results from the 4 daily SMBG measures to fulfill these criteria. Every fourteen/ten (10/14) days the sensor needs to be replaced and subjects can return to the site for assistance on this if needed. If the subject needs assistance with sensor replacement, an ad-hoc visit should be performed, if this occurs a data upload is also recommended at this time. If subjects opt to perform sensor replacement at home sites should call subject 7 days after insertion as a reminder.

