**Table 4: Variable in cgmanalysis**

Endpoint	Variable in cgmanalysis	Unit
TIR	percent_time_70_180	%
Glucose AUC outside the target range of 70/180 mg/dL	average_auc_70 + average_auc_180	mg/dL/min
MAGE (1 SD)	r_mage	mg/dL
CONGA-1, CONGA-2 and CONGA-4	conga_1, conga_2, conga_4	mg/dL
MODD	modd	mg/dL
Mean daily blood glucose	average_sensor	mg/dL
SD	standard_deviation	mg/dL
2h-PPG	average_auc_per_day*	mg/dL

*\*raw data must be filtered with observations  $\leq$  120 minutes from meals (eDiary)*

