# PPD

R code	Notes
<pre> }  # Total AUC. sensorBG <- base::as.numeric(table\$sensorglucose,length = 1) xaxis <-   base::seq(from = 0, length.out = base::length(sensorBG),by =   (interval / 60))  # Remove NAs if they are present. xaxis[base::which(is.na(sensorBG))] <- NA xaxis <- xaxis[!is.na(xaxis)] sensorBG <- sensorBG[!is.na(sensorBG)] aucs <- pracma::cumtrapz(xaxis,sensorBG) cgmupload["total_auc",f] <- aucs[base::length(sensorBG)]  cgmupload["average_auc_per_day",f] <-   base::as.numeric(cgmupload["total_auc",f]) /   base::as.numeric(cgmupload["num_days_good_data",f])  # AUC over 180. sensorover180 <- table\$sensorglucose sensorover180 <- sensorover180[sensorover180 >= 180] sensorover180 <- sensorover180[!is.na(sensorover180)] xaxis <-   base::seq(from = 0, length.out = base::length(sensorover180),by =   (interval / 60))  # Calculate cumulative AUC, and subtract rectangle where length = 180 & # width = minutes. if (base::length(sensorover180) > 1) {   aucs <- pracma::cumtrapz(xaxis,sensorover180)   aucs <-     (aucs[base::length(sensorover180)]) - (xaxis[base::length(xaxis)] * 180)   cgmupload["auc_over_180",f] <- aucs } else {   cgmupload["auc_over_180",f] <- 0 } cgmupload["average_auc_180",f] <-   base::as.numeric(cgmupload["auc_over_180",f]) /   base::as.numeric(cgmupload["num_days_good_data",f]) </pre>	
<pre> # AUC lower 70. sensorlower70 <- table\$sensorglucose sensorlower70 <- sensorlower70[sensorlower70 < 70] sensorlower70 <- sensorlower70[!is.na(sensorlower70)] xaxis <-   base::seq(from = 0, length.out = base::length(sensorlower70),by =   (interval / 60)) </pre>	This section has been modified in order to calculate the AUC between 70 (upper limit) and the glucose curve (lower limit).

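### The 2-hour postprandial glucose index in SAP Table 4 is an area divided by a rounded reading count, not a value in mg/dL, and it changes with the number of timed meals

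*SAP*

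**What the plan says.** 2h-PPG is one of the secondary CGM indices (Protocol 4.1). SAP 7.2.1.7 compares it between arms by t-test or Mann-Whitney test.

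SAP 9.2 sets the input: "For the calculation of 2h PPG, the raw data from Dexcom G6 System have to be filtered in order to keep only observations" no more than 120 minutes from breakfast, lunch or dinner, with meal times taken from the diary. It adds: "If time of meal is missing, the adjacent CGM observations will not be considered".

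Table 4 maps 2h-PPG to "average_auc_per_day" on the filtered data, unit mg/dL. In the same table, glucose AUC outside the target range is "average_auc_70 + average_auc_180", with a unit that contains minutes.

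In Appendix 12.1 the numerator of `average_auc_per_day` is the last value of "pracma::cumtrapz(xaxis,sensorBG)", with the x-axis in minutes. The divisor is `num_days_good_data`, which is the number of non-missing readings divided by "86400/interval" and rounded to a whole number. On recording frequency, Protocol 14.3.4 states: "The system records data approximately every 5 minutes".

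**The concern.** An area in mg/dL × min divided by a count is not a concentration, so the unit in Table 4 cannot be right. The divisor is the more serious problem. On a full CGM file, `num_days_good_data` approximates days of recording. On a file holding only post-meal windows it is a small integer that steps up at rounding thresholds. The area grows with each timed meal, while the divisor stays flat and then jumps.

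The reported value would therefore reflect diary completeness and days of wear as well as glucose. Two patients with the same post-meal glucose could differ markedly, and a patient with lower glucose could rank above one with higher glucose. If the implausible size were noticed only at output review, correcting it then would be an unplanned change.

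**Working it through.** **Inputs**
- Recording interval of 5 minutes (Protocol 14.3.4), so 86,400/300 = 288 readings per day.
- Window of 0 to 120 minutes after a meal, so 24 or 25 readings per meal, depending on whether both ends are counted (assumption).
- Three meals a day (SAP 9.2) over 7 to 14 days, so 21 to 42 timed meals. Seven days is the SAP 9.2 minimum for a usable visit, and Protocol 14.3.4 places the sensor 14 to 10 days before the visit.
- Constant post-meal glucose G, to isolate the arithmetic. Ratios do not depend on G.

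**Formula from Appendix 12.1**, with n retained readings:
- `total_auc` = G × 5 × (n − 1)
- `num_days_good_data` = round(n/288)
- `average_auc_per_day` = G × 5(n − 1)/round(n/288)

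**Unit check.** There is no planned numerical value to reproduce; the stated item is the unit. The multiplier on G is as follows:
- 25 readings per meal: lowest 1,206.7 (29 meals), highest 1,747.5 (28 meals).
- 24 readings per meal: lowest 1,238.3 (31 meals), highest 1,737.5 (29 meals). This leaves out 30 and 42 meals, where n/288 ends in exactly .5.

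So 150 mg/dL is reported as about 181,000 to 262,000. The protocol's own target for 2-hour postprandial glucose is below 180 mg/dL.

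**Dependence on meal count at a constant 150 mg/dL**

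| Readings per meal | Timed meals | n | n/288 | Divisor | Output |
|---|---|---|---|---|---|
| 25 | 28 | 700 | 2.43 | 2 | 524,250/2 = 262,125 |
| 25 | 29 | 725 | 2.52 | 3 | 543,000/3 = 181,000 |
| 24 | 29 | 696 | 2.42 | 2 | 521,250/2 = 260,625 |
| 24 | 31 | 744 | 2.58 | 3 | 557,250/3 = 185,750 |

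The ratios are 262,125/181,000 = 1.45 and 260,625/185,750 = 1.40. A further step comes at 40 to 41 meals with 25 readings: the multiplier falls from 1,665 to 1,280, or 23%.

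**Days of wear alone.** With every meal timed and 25 readings per meal, 9 days (27 meals) give 252,750 and 10 days (30 meals) give 187,250, a 35% spread. With 24 readings, leaving out the ties at 10 and 14 days, the spread is 29%.

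**Rank reversal.** With 25 readings per meal, constant 150 mg/dL with 28 meals gives 262,125, and constant 200 mg/dL with 29 meals gives 200 × 1,206.67 = 241,333. The second patient would need more than 150 × 1,747.5/1,206.67 = 217 mg/dL to rank higher. With 24 readings and 29 versus 31 meals, the break-even is 150 × 1,737.5/1,238.33 = 210 mg/dL.

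**Comparison variable.** `average_sensor`, the plain mean in the same function, returns 150 in every row of the table above.

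**The case against.** The strongest reply concerns size. Across all 231 pairs of meal counts from 21 to 42 with 25 readings per meal, only 28 versus 29 reaches 40%. The median difference is 12%, and most neighbouring counts differ by 2 to 5%. This stands: 40 to 45% is what can happen, not what is typical.

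The SAP also says within 120 minutes from meals without saying after. If the window is 120 minutes on either side (49 readings), the largest spread over 21 to 42 meals is 24% and the median 6%. That sits poorly with a postprandial index, and the output is still more than 1,000 times the glucose level.

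A third point is that the meal filter is not printed in the appendix, so the divisor might come from the unfiltered file. The rounding jumps would then largely go, but the output would still be an area that grows with timed meals. At 160 mg/dL, 25 readings per meal and a 10-day divisor, it is 160 × 5 × 599/10 = 47,920 for 24 meals and 160 × 5 × 749/10 = 59,920 for 30. The printed function takes numerator and divisor from one file.

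Table 4's other unit, mg/dL/min, is also wrong for an area, so it is weak evidence of intent. It does show that two variables built the same way carry different units.

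Finally, nothing in the documents suggests that timed-meal counts differ by arm under blinding. The expected effect is added noise in the arm comparison, not demonstrated bias.

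**Conclusion.** The point holds. As written, the 2h-PPG variable is not in mg/dL under any reading of the window or the divisor, and it varies with the number of timed meals. Under the more natural reading (readings after the meal, one file for numerator and divisor, 5-minute recording, 21 to 42 timed meals), identical glucose can give values 40 to 45% apart at the worst pairs of meal counts, with a median difference of about 12%. Relabelling the unit would leave this in place.

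This should be fixed, but its reach is limited. It concerns one secondary CGM index, all efficacy analyses are descriptive after the early closure (SAP 4.8 and 7), and the primary endpoint is not touched.

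**What to change.** - In Table 4, map 2h-PPG to `average_sensor` computed on the meal-filtered file, unit mg/dL.
- In SAP 9.2, define the index as mean glucose from 0 to 120 minutes after timed meals. This settles the window. If the sponsor intends another definition, such as the value at two hours, it should be stated there instead.
- In SAP 9.2, state that the rules of at least 7 valid days and more than 80% wear are checked on the unfiltered file. The filtered file cannot meet them: 30 meals of 25 readings give round(750/288) = 3 days and 750/2,880 = 26% of ten days' readings.
- Report the number of meals used per visit and arm.

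The cost is one table row, two sentences and a meal-count line in one table shell. `average_sensor` is already output, and the meal filter has to be programmed in any case. No new data are needed.
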